# 12.4 Analysis of the primary endpoint(s)

## 12.4.1 **Definition of primary endpoint(s)**

The primary aim of the study is to evaluate the long-term safety of 70 and 140 mg erenumab in patients with episodic or chronic migraine. The primary endpoint variable is the exposure adjusted incidence rate of AEs during the open-label treatment epoch per 100 subject years.Statistical model, hypothesis, and method of analysis

The primary analyses will be conducted dividing the number of AEs by the time under treatment and standardizing it per 100 person-years. Exact Pearson-Clopper confidence intervals for single proportions will be calculated in order to evaluate the precision of the estimated parameter. No formal hypotheses testing will be conducted.

#### 12.4.2 Handling of missing values/censoring/discontinuations

For every patient, it can be determined whether he/she discontinued for AE-related reasons. Non-AE-related discontinuations or losses to follow up will not be counted as AE-related discontinuations. AE-related discontinuations are counted as events, discontinuation due to other reasons are not counted as events.

#### 12.4.3 **Sensitivity analyses**

#### Sensitivity analyses

The primary analysis will also be conducted within the subgroups defined by sex, disease severity and prior treatment failure status (naïve vs. prior treatment failures). The primary analysis will also be repeated for all- cause treatment discontinuations (instead of AE-related).

#### Supportive analyses

## 12.5 Analysis of secondary endpoints

To evaluate the long-term tolerability of 70 and 140 mg erenumab in patients with episodic or chronic migraine.

#### 12.5.1 Efficacy and/or Pharmacodynamic endpoint(s)

- Proportion of patients discontinuing open-label treatment epoch due to AE
- Proportion of patients discontinuing open-label treatment epoch due to non-AE reasons

#### 12.5.2 Safety endpoints

For all safety analyses, the safety set will be used. All listings and tables will be presented.

Safety summaries (tables, figures) include only data from the on-treatment period with the exception of baseline data which will also be summarized where appropriate (e.g. change from baseline summaries). In addition, a separate summary for death including on treatment and post treatment deaths will be provided. In particular, summary tables for adverse events (AEs) will summarize only on-treatment events, with a start date during the on-treatment period (treatment-emergent AEs).

The on-treatment period lasts from the date of first administration of study treatment to 112 days after the date of the last actual administration of study treatment.

#### Adverse events

All information obtained on adverse events will be displayed and subject.

The number (and percentage) of subjects with treatment emergent adverse events (events started after the first dose of study medication or events present prior to start of treatment but increased in severity based on preferred term) will be summarized in the following ways:

- by primary system organ class and preferred term.
- by primary system organ class, preferred term and maximum severity
- by Standardized MedDRA Query (SMQ) and preferred term

Novartis	Confidential	Page 51
Clinical trial protocol V01	Protocol No. CAMG334ADE03	

Separate summaries will be provided for study medication related adverse events, death, serious adverse events, other significant adverse events leading to discontinuation and adverse events leading to dose adjustment.

The number (and proportion) of subjects with adverse events of special interest will be summarized.

A subject with multiple adverse events within a primary system organ class is only counted once towards the total of the primary system organ class.

#### Vital signs

All vital signs data will be listed by subject, and visit/time and if ranges are available, abnormalities (and relevant orthostatic changes) will be flagged. Summary statistics will be provided by visit/time.

#### 12-lead ECG

All ECG data will be listed by subject and visit/time, abnormalities will be flagged. Summary statistics will be provided.

#### **Clinical laboratory evaluations**

All laboratory data will be listed by subject, and visit/time and if normal ranges are available abnormalities will be flagged. Summary statistics will be provided by visit/time. Shift tables using the low/normal/high/ (low and high) *(or project specific)* classification will be used to compare baseline to the worst on-treatment value.

## 12.7 Interim analyses

Not applicable.

# 12.8 Sample size calculation

In general, the 750 subjects randomized for clinical trial CAMG334ADE01 will be eligible for participation in the open-label study. It is estimated that approximately 75% to 85% of the study population meaning 563~638 subjects will enroll in the open-label study thus allowing the collection of long-term safety, efficacy and quality of life data of a large group of patients.

#### 12.8.1 **Primary endpoint(s)**

In the three-year open-label phase II study 20120178 the proportion of patients reporting at least one AE was 87%. Based on this finding the following event rates and precisions were calculated for the proposed 128-week trial for the primary endpoint in Table 1.

Sample size	Proportion any AE	Precision (+/-)
500	70%	4.0%
	80%	3.5%
	85%	3.1%
	90%	2.6%

Table 1: Proportion of event and precision primary endpoint: Any AE

In conclusion a study population of at least 500 patients was found to be sufficient for the primary endpoint with an adequate range in precision.

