2.1.1.1 Study dates

First IMP Dose Date

The first IMP dose date is the date on which a subject is administered the first dose of erenumab following screening. For subjects who are screened but no dose administration is documented, first IMP Dose Date is considered missing.

Last IMP Dose Date

The last IMP dose date for each subject is defined as the latest date of a dose administration.

Time under treatment

Time under treatment is defined as (Last IMP Dose Date + 28 – First IMP Dose Date) - Duration of treatment interruption due to drug holiday (if applicable).

Exposure-adjusted incidence rate of AE

Exposure-adjusted patient incidence rate of AE is defined as the total number of patients who reported an AE in a given time period of follow up divided by total patient-years of exposure in that period.

Total patient-years of exposure is defined as the sum of the duration of exposure from first IMP dose to the earliest of end-of-study date, end-of-OLTP date, or first report of event across all patients during the OLTP.

Study Day

Study Day 1 is defined as the first IMP dose date. For patients who are screened but not dosed after inclusion, Study Day 1 is defined as the date of screening visit.

Study Day is defined as the number of days from Study Day 1.
Before Study Day 1:
Study Day = (Date of Interest – Date of Study Day 1)

On or after Study Day 1: Study Day = (Date of Interest – Date of Study Day 1) + 1

Therefore the day prior to Study Day 1 is Day -1.

Drug holiday

Drug holiday is defined as a voluntary single treatment interruption of up to 24 weeks introduced after at least 12 weeks of treatment in the open-label Treatment Epoch.

After the "Planned date of last dose before drug holiday" starts a 28 day drug holiday initiation period, followed by the actual drug holiday period (see definitions below).

Drug holiday planned

Drug holiday is defined as planned if in the eCRF "Planned date of last dose before drug holiday" is not missing.

Drug holiday started

Drug holiday is defined as started if in the eCRF "Planned date of last dose before drug holiday" is not missing and lies at least 4 weeks before the cut-off date (regarding the interim analysis) resp. end of study date and up to day 28 after the "Planned date of last dose before drug holiday" no IMP application is documented.

Return to treatment after drug holiday

Patients are defined as returned after drug holiday if in the eCRF "Date of first dose after drug holiday" is not missing.

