2.5.2 Statistical hypothesis, model, and method of analysis

The primary analyses will be conducted dividing the number of AEs by the time under treatment and standardizing it per 100 person-years. Exact Pearson-Clopper confidence intervals for single proportions will be calculated in order to evaluate the precision of the estimated parameter. No formal hypotheses testing will be conducted.

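### Protocol 12.8.1 Table 1 gives the precision of a patient proportion but presents it as that of the primary AE rate per 100 subject-years, for which no precision is stated

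*Protocol*

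**What the plan says.** Protocol 12.4.1 defines the endpoint as a rate: "The primary endpoint variable is the exposure adjusted incidence rate of AEs during the open-label treatment epoch per 100 subject years". Protocol Table 2-1 and SAP 1.2 and 2.5.1 agree. For estimation, protocol 12.4.1 states: "The primary analyses will be conducted dividing the number of AEs by the time under treatment and standardizing it per 100 person-years". SAP 2.5.2 repeats this. Both sections then specify the interval: "Exact Pearson-Clopper confidence intervals for single proportions will be calculated in order to evaluate the precision of the estimated parameter". Neither plans a hypothesis test.

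SAP 2.1.1.1 has its own entry for the exposure-adjusted rate: the "total number of patients who reported an AE in a given time period of follow up divided by total patient-years of exposure". In that entry each patient's exposure stops at the first event, the end of the open-label period or the end of study, whichever is earliest.

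The sample-size argument in protocol 12.8.1 begins from a proportion: "In the three-year open-label phase II study 20120178 the proportion of patients reporting at least one AE was 87" per cent. It then tabulates proportions of 70, 80, 85 and 90% at N = 500, under the title "Table 1: Proportion of event and precision primary endpoint: Any AE", and closes with this statement: "In conclusion a study population of at least 500 patients was found to be sufficient for the primary endpoint with an adequate range in precision". SAP 3 repeats the argument and the conclusion without the table. Expected enrolment is 563 to 638.

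**The concern.** A proportion of patients and a rate per unit of time are different parameters in different units. A half-width of 3 percentage points says nothing direct about the width of an interval around a figure such as 80 AEs per 100 subject-years. Because no hypothesis is tested, the rate and its interval are the whole primary result, and Table 1 is the only statement that the trial is large enough to estimate it. Tables 2 and 3 serve the secondary discontinuation endpoints.

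The interval specification carries the problem into the analysis. A number of AEs divided by person-time is not a binomial proportion. If AEs outnumber patients, a single-proportion interval with patients as the denominator cannot be formed. If the interval is instead meant for the proportion of patients with an AE, it is valid for that proportion, but then the primary rate has no planned interval.

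**Working it through.** **Inputs.** From protocol 12.8.1: N = 500, the four proportions, and 87% of patients with an AE over three years. From protocol 6.1.4: 128 weeks of treatment, so T = 128 × 7 / 365.25 = 2.453 years. From protocol 12.8: enrolment of 563 to 638. Assumed, because the documents do not give them: 95% confidence, constant hazard or rate over time, complete follow-up, and the distribution of AE counts between patients.

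**Step 1: reproduce Table 1.** Half-width = 1.96 × sqrt(p(1 − p)/500).

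| p | Computed (points) | Table 1 |
|---|---|---|
| 70% | 4.02 | 4.0 |
| 80% | 3.51 | 3.5 |
| 85% | 3.13 | 3.1 |
| 90% | 2.63 | 2.6 |

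All four rows match. The formula contains no exposure time. Exact Clopper-Pearson limits would give mean half-widths of 4.11, 3.60, 3.23 and 2.73, so the table is a Wald calculation.

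**Step 2: first-event rate (SAP 2.1.1.1).** With constant hazard and all 500 patients followed for 128 weeks, rate = −ln(1 − p)/T, first events = 500p, and subject-years = events/rate. The interval is exact Poisson. The last column puts Table 1's own limits through −ln(1 − p)/T.

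| p | Events | Subject-years | Rate per 100 | 95% limits | Half-width | Table 1 converted |
|---|---|---|---|---|---|---|
| 70% | 350 | 713 | 49.1 | 44.1–54.5 | 5.2 | 5.5 |
| 80% | 400 | 610 | 65.6 | 59.3–72.4 | 6.5 | 7.2 |
| 85% | 425 | 550 | 77.3 | 70.2–85.0 | 7.4 | 8.6 |
| 90% | 450 | 479 | 93.9 | 85.4–103.0 | 8.8 | 11.0 |

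Under this definition Table 1 can be converted and lands close to the right answer, erring on the wide side. The documents do not make the conversion.

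**Step 3: all-AE rate (protocol 12.4.1, SAP 2.5.2).** Take 87% with at least one AE by three years, with complete follow-up. If counts are Poisson, the yearly rate is −ln(0.13)/3. If patient rates vary as a gamma with shape k, it is k(0.13^(−1/k) − 1)/3. The mean count per patient over 128 weeks is m = rate × T, with variance v = m + m²/k (v = m for Poisson). Half-width per 100 subject-years = 100 × 1.96 × sqrt(v/N)/T. At N = 500 exposure is 500 × 2.453 = 1,227 subject-years.

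| Assumption | Rate per 100 | m | v | AEs in 500 | Half-width, N = 500 | N = 563 to 638 |
|---|---|---|---|---|---|---|
| Poisson | 68 | 1.668 | 1.668 | 834 | 4.6 | 4.3 to 4.1 |
| Gamma, k = 2 | 118 | 2.900 | 7.107 | 1,450 | 9.5 | 9.0 to 8.4 |
| Gamma, k = 1 | 223 | 5.472 | 35.42 | 2,736 | 21.3 | 20.0 to 18.8 |

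In these three cases the proportion with an AE by week 128 is 81.1, 83.3 and 84.5%, so Table 1's formula gives nearly the same answer each time: 3.4, 3.3 and 3.2 points. The half-width of the rate differs more than fourfold (21.3/4.6). Table 1 cannot tell these cases apart. In each of them AEs outnumber the 500 patients.

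**The case against.** The best defence is that the proportion of patients with any AE is a familiar planning surrogate, and that nothing in the design turns on Table 1. Enrolment is bounded by the 750 patients of the parent trial, 563 to 638 are expected, 500 is only a floor, and no test is planned. The SAP also reports subject incidence of AEs, so Table 1 describes the precision of something that will be reported. Under the SAP's explicit definition of the rate, it even converts to about the right width. All of this stands, and it limits the point to one of specification.

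It does not remove the point. Protocol 12.8.1 does not call the proportion a surrogate; it says the precisions were calculated for the primary endpoint. The conversion works only for the first-event definition, while both analysis sections count AEs. A planning surrogate also does not explain a single-proportion interval in the analysis itself.

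A reader might go further and infer that 500 patients are too few. The documents do not support that. They set no target precision, and in the illustrations above the half-width is only about 7 to 11% of the rate.

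A reader might also want to refine the 87% using the discontinuations in protocol 12.8.2. That section gives 22.2% for non-AE reasons only after replacing the observed patient requests with smaller numbers, over three years rather than 128 weeks. It does not give the follow-up needed for such a correction, so none is attempted here.

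**Conclusion.** The point holds as a mismatch of parameter, in the sample-size statement and in the planned interval. Table 1 is arithmetically correct for the proportion of patients with at least one AE and mislabelled as the precision of the primary rate. No precision for that rate appears in either document. The mismatch exists under both definitions of the rate, since both divide by person-time.

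The size can only be illustrated. At N = 500 the half-width is 5.2 to 8.8 per 100 subject-years for a first-event rate (70 to 90% of patients with an AE), and 4.6, 9.5 or 21.3 for an all-AE rate consistent with 87% by three years. These figures rest on 95% confidence, constant hazard and complete follow-up. The gamma shapes are assumptions with no source in the documents. Dropout, and drug holidays where time under treatment is the denominator, would reduce exposure and widen the intervals at a given rate. The adequacy of 500 patients is not in question; what the plan lacks is a valid interval and a precision statement for its own primary result.

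**What to change.** Keep the sample size and make three changes.

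1. Reconcile protocol 12.4.1 and SAP 2.5.2 with SAP 2.1.1.1, so that one numerator and one denominator define the primary rate. Replace the Clopper-Pearson interval with a person-time interval at a stated confidence level: exact Poisson for a first-event rate, or a variance that allows repeated AEs within a patient for an all-AE rate.
2. Retitle Table 1 as the 95% half-width for the proportion of patients with at least one AE.
3. In protocol 12.8.1 and SAP 3, replace the claim of sufficiency for the primary endpoint with the expected 95% half-width of the chosen rate at N = 500 and at N = 563 to 638. Show it over a stated range of rate, exposure (after dropout and, if time under treatment is used, drug holidays) and overdispersion.

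The cost is one table title, the sample-size sentence and the interval sentence in each document, the reconciled rate definition, and a short calculation. No patients, visits or assessments are added. The sponsor must supply an AE rate and an overdispersion value, or a plausible range for each, because the documents contain neither. The new half-width will be in AEs (or first events) per 100 subject-years and will not be directly comparable with Table 1's percentage points.

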## 12.8.2 **Secondary endpoint(s)**

The calculation of effect size and precision for the secondary endpoints is based on the proportion of study discontinuation rates in the three-year open-label phase II study 2012017. 4.2% of 383 patients discontinued this trial due to adverse events. Table 2 shows the effect size and precision for the proposed study with at least 500 patients.

Sample size	Proportion any AE	Precision (+/-)
500	5%	1.9%
	10%	2.6%
	15%	3.1%

Table 2: Proportion of event and precision secondary endpoint: AE-related discontinuation

Among the non-AE related study discontinuations the group 'upon patient request' was particularly high at the time point of erenumab marketing authorization. 68 patients requested study discontinuation in the first two years of the open-label study overlapping with marketing authorization. In the following 12 months 8 patients requested study discontinuation. In order to use more realistic number as basis for the effect calculations of the proposed study patient discontinuation rates after marketing authorization were utilized. This number was multiplied by three to account for the longer duration of the first part of the study and to add an additional buffer for uncertainty. This means, 24 patient requests for study discontinuation in the first two years and 8 requests in the third year were included in the calculation. Overall, this results in a discontinuation rate due to any non-AE reasons of 22.2%. Table 3 shows the estimated event rates and precisions for this secondary endpoint.

Table 3: Proportion of event and precision secondary endpoint: non AE-related discontinuation

Sample size	Proportion any AE	Precision (+/-)
500	15%	3.1%
	20%	3.5%
	25%	3.8%

In conclusion a study population of at least 500 patients was found to be sufficient for the secondary endpoints with an adequate range in precision.

# 13 Ethical considerations and administrative procedures

## 13.1 Regulatory and ethical compliance

This clinical study was designed and shall be implemented, executed and reported in accordance with the ICH Harmonized Tripartite Guidelines for Good Clinical Practice, with applicable local regulations (including European Directive 2001/20/EC, US CFR 21), and with the ethical principles laid down in the Declaration of Helsinki.

# 13.2 **Responsibilities of the investigator and IRB/IEC**

Before initiating a trial, the investigator/institution must obtain approval/favorable opinion from the Institutional Review Board/Independent Ethics Committee (IRB/IEC) for the trial protocol, written informed consent form, consent form updates, subject recruitment procedures (e.g., advertisements) and any other written information to be provided to subjects. Prior to study start, the investigator is required to sign a protocol signature page confirming his/her agreement to conduct the study in accordance with these documents and all of the instructions and procedures found in this protocol and to give access to all relevant data and records to Novartis monitors, auditors, Novartis Quality Assurance representatives, designated agents of Novartis , IRBs/IECs, and regulatory authorities as required. If an inspection of the clinical site is requested by a regulatory authority, the investigator must inform Novartis immediately that this request has been made.

# 13.3 **Publication of study protocol and results**

The protocol will be registered in a publicly accessible database such as clinicaltrials.gov and as required in EudraCT. In addition, after study completion (defined as last patient last visit) and finalization of the study report the results of this trial will be submitted for publication and posted in a publicly accessible database of clinical trial results, such as the Novartis clinical trial results website and all required Health Authority websites (e.g. Clinicaltrials.gov, EudraCT etc.).

For details on the Novartis publication policy including authorship criteria, please refer to the Novartis publication policy training materials that were provided to you at the trial investigator meetings.

# 13.4 **Quality Control and Quality Assurance**

Novartis maintains a robust Quality Management System (QMS) that includes all activities involved in quality assurance and quality control, to ensure compliance with written Standard Operating Procedures as well as applicable global/local GCP regulations and ICH Guidelines.

Audits of investigator sites, vendors, and Novartis systems are performed by auditors, independent from those involved in conducting, monitoring or performing quality control of the clinical trial. The clinical audit process uses a knowledge/risk based approach.

Audits are conducted to assess GCP compliance with global and local regulatory requirements, protocols and internal SOPs, and are performed according to written Novartis processes

# 14 **Protocol adherence**

This protocol defines the study objectives, the study procedures and the data to be collected on study participants. Additional assessments required to ensure safety of subjects should be administered as deemed necessary on a case by case basis. Under no circumstances including incidental collection is an investigator allowed to collect additional data or conduct any additional procedures for any purpose involving any investigational drugs

Novartis	Confidential	Page 55
Clinical trial protocol V01	Protocol No. CAMG334ADE03	-

under the protocol, other than the purpose of the study. If despite this interdiction prohibition, data, information, observation would be incidentally collected, the investigator shall immediately disclose it to Novartis and not use it for any purpose other than the study, except for the appropriate monitoring on study participants.

Investigators ascertain they will apply due diligence to avoid protocol deviations. If an investigator feels a protocol deviation would improve the conduct of the study this must be considered a protocol amendment, and unless such an amendment is agreed upon by Novartis and approved by the IRB/IEC and health authorities, where required, it cannot be implemented.

